2.1. Primary objective

Evaluate the health literacy of cancer patients using the approved French version of the Functional, Communicative and Critical Health Literacy (FCCHL) scale in 2 populations:

- Population A: patients age 65 and over treated in an oncology or oncogeriatric outpatient clinic, or seen in an oncology or oncogeriatric consultation.
- Population B: young patients age 18 to 64 treated in an oncology or outpatient clinic, or seen in an oncology consultation.

2.2. Secondary objectives

- Describe the digital health literacy of patients per population.
- Identify groups with low health literacy and evaluate the related factors (age, sex, lifestyle etc.).
- Explore the factors related to the use of the digital.

3. Study organisation

3.1. Study design

- Multicentric, prospective, observational, transversal study.

3.2. Study size

- Total : 840 patients
 - Population A : 420 patients
 - Population B : 420 patients

The primary endpoint is the percentage of participants with an overall score of ≤ 4 on the FCCHL scale, evaluated in 2 populations.

- Population A: patients age 65 and over treated in an oncology or oncogeriatric outpatient clinic, or seen in an oncology or oncogeriatric consultation.
- Population B: young patients age 18 to 64 treated in an oncology or outpatient clinic, or seen in an oncology consultation.
- We plan to include around 300 eligible and assessable patients (overall score available) for the primary endpoint in each of the two populations (A and B). A total of 420 patients per population will be included in this study in order to take account of 40% of non-eligible/non-assessable patients (score not available – 35%) of patients had not fully completed the questionnaire in the feasibility study).

4. Definition of analysis populations

4.1. Analysis populations

Eligible population: all the patients included without major deviation from the eligibility criteria.

Eligible and assessable population: eligible patients having a completed all 14 items on the FCCHL scale to calculate the overall health literacy score.

5. Eligibility criteria

5.1. Inclusion criteria

Criteria	eFORM variable	Control
1. Man or women	SEXE	SEXE in (1 2)
2. Age \geq 18 years	AGE	AGE \geq 18
3. Patient treated for cancer	LOC_CAN__X	X= 1 à 21 LOC_CAN__X=1 or LOC_CAN__X=1
4. Patient who can read and understand French	NA	Investigator decision
5. Patient seen in an oncology or oncogeriatric consultation or treated in an outpatient clinic.	LIEU	LIEU in (1 2 3)
6. Patient in treatment or about to start treatment that has been offered to them, from the announcement consultation to 2 years after the start of treatment	TRT_CAN__1 TRT_CAN__2 TRT_CAN__3 TRT_CAN__4 TRT_CAN__5 TRT_CAN__6 TRT_CAN__7 TRT_CAN__8	TRT_CAN__1=1 or TRT_CAN__2=1 or TRT_CAN__3=1 or TRT_CAN__4=1 or TRT_CAN__5=1 or TRT_CAN__6=1 or TRT_CAN__7=1 or TRT_CAN__8=1

5.2. Exclusion criteria

Criteria	eFORM variable	Control
1. Patient hospitalised for longer than 24 hours.	NA	Investigator decision
2. Patient with known cognitive impairment preventing them from answering the questionnaire	NA	Investigator decision

*NA : not applicable

6. Data statistical analysis

6.1. Descriptive methods

6.1.1. Quantitative variables

Quantitative variables will be described based on the mean and standard-deviation if the assumption of normality is followed, otherwise other descriptive statistics will be used (minimum, maximum, median and quartile)

6.1.2. Qualitative variables

The qualitative variables will be described base on numbers and associated frequencies, given as a percentage (%).

6.2. Confidence interval

The percentage of patients with a low level of health literacy will be reported along with its 95% confidence interval (binomial law).

6.3. Analysis methods

6.3.1. Sensitivity analysis

Sensitivity analyses could be carried out by varying the discrimination threshold for a low level of health literacy (currently global score ≤ 4 = low level of literacy).

6.3.2. Exploratory analysis

Statistical tests will be carried out (chi-square test or Fisher's exact test) to analyse the associations between low health literacy and patient characteristics at inclusion. Univariate and multivariate analyses will also be carried out.

8. Statistical analysis

Analysis population :

- Eligible population: all the patients included without major deviation from the eligibility criteria.
- Eligible and assessable population: eligible patients having completed all 14 items on the FCCHL scale to calculate the overall health literacy score.

Primary endpoint analysis :

- The primary endpoint analysis will cover the eligible, assessable population.
- The analyses will be conducted independently in each of the two populations A and B.
- The percentage of patients with a low level of health literacy will be calculated as follows:
 - Each item on the FCCHL takes a score of 1 to 5 points.
 - For each patient, a literacy score per sub-scale (functional, interactive and critical) will be determined by calculating the number of points divided by the number of items on the sub-scale. The score can range from 1 to 5.
 - An overall literacy score will be calculated for each patient, by determining the mean of the functional, interactive and critical literacy scores. The score can range from 1 to 5.
 - The percentage of patients with a low level of health literacy will be calculated for each population (A, B), by dividing the number of patients with an overall score of ≤ 4 by the number of eligible and assessable patients. The percentage will be reported along with its 95% confidence interval (binomial law).
- The responses to the FCCHL scale will be described for each population (A, B) by sub-scale and overall, by calculating the mean and the standard-deviation of the 4 literacy scores (functional; interactive, critical and overall) resulting for each patient.
- The quantitative variables will be described based on the mean and standard-deviation if the assumption of normality is followed, otherwise other descriptive statistics will be used (minimum, maximum, median and quartile).
- The qualitative variables will be described based on numbers and associated frequencies, given as a percentage (%).

9. Outcome measures

9.1. Primary endpoint

The primary endpoint is the percentage of participants with an overall score of ≤ 4 on the FCCHL scale, corresponding to a low level of health literacy:

- The FCCHL questionnaire includes 14 items, divided into 3 sub-scales, reflection 3 health literacy skills (functional literacy, interactive literacy and critical literacy).
- The FCCHL is validated and a French translation is available.
- The score for the tree sub-scales are described for each population, and an overall score will be calculated by determining the mean score for the 3 sub-scales.
- An overall score of ≤4 points to a low level of literacy

Criteria	eFORM variable	SAS code
Percentage of patients with an overall score ≤4 on the FCCHL scale corresponding to a low level of health literacy		SCORE_GLO = mean(score_fonc, score_int, score cri) TAUX=SCORE_GLO/EVA

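### Minor: the SAS line for the primary endpoint in SAP 9.1 returns a patient's score, not the percentage with an overall score ≤4

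*SAP*

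**What the plan says.** The table in SAP 9.1 has a column for SAS code. Its single row is labelled "Percentage of patients with an overall score ≤4 on the FCCHL scale corresponding to a low level of health literacy". The code beside the label first sets `SCORE_GLO` to the mean of the functional, interactive and critical scores, and then "TAUX=SCORE_GLO/EVA".

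SAP section 8 defines the percentage in words, as obtained "by dividing the number of patients with an overall score of ≤ 4 by the number of eligible and assessable patients". It also fixes the analysis set ("The primary endpoint analysis will cover the eligible, assessable population") and the grouping ("The analyses will be conducted independently in each of the two populations A and B"). SAP 6.2 adds a binomial 95% confidence interval. The protocol's statistical analysis section gives the same definition.

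SAP Appendice 2 derives `EVA` for each patient. It is 1 when the patient is eligible and all 14 FCCHL items are present, and 0 otherwise. The appendices derive the eligibility and assessability flags, but no variable for low literacy.

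**The concern.** The code cell and the definition it is meant to implement do not agree. The definition counts patients at or below a cut-off of 4 and divides by the number of assessable patients. The code contains no comparison with 4 and no count.

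This is the only code the SAP gives for its only primary endpoint. Programmed as written, it would not produce the primary result.

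The missing low-literacy variable is also needed elsewhere. SAP 6.3.2 plans tests "to analyse the associations between low health literacy and patient characteristics at inclusion", and SAP 6.3.1 allows an optional analysis: "Sensitivity analyses could be carried out by varying the discrimination threshold for a low level of health literacy". One correct derivation would serve all three.

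**Working it through.** **Inputs**
- `SCORE_GLO`: one value per patient, from 1 to 5 (SAP 9.1 and section 8).
- `EVA`: one 0/1 value per patient (SAP Appendice 2).
- Defined endpoint: number of patients with score ≤4 / number eligible and assessable, in A and B separately (SAP section 8).

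**The plan's own figures.** The documents give no figure for `TAUX`. They do give a precision table for 300 assessable patients per population. The Wald half-width 1.96 × √(p(1−p)/300) reproduces it:

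| p | Half-width, points | Plan |
|---|---|---|
| 60% | 5.54 | 5.5 |
| 70% | 5.19 | 5.2 |
| 80% | 4.53 | 4.5 |
| 90% | 3.39 | 3.4 |

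The study is therefore sized for a proportion, which is what section 8 defines and what the code cell does not compute.

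**Reading 1: patient by patient.** For an assessable patient `EVA`=1, so `TAUX` = `SCORE_GLO`/1 = `SCORE_GLO`. For a patient with `EVA`=0 the line divides by zero and has no value.

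**Reading 2: ratio of sums.** Over assessable patients, sum(`SCORE_GLO`)/sum(`EVA`) is the mean score. The mean does not determine the share at or below 4:
- Scores {3, 5}: (3+5)/2 = 4.0; share ≤4 is 1/2 = 50%.
- Scores {4, 4}: (4+4)/2 = 4.0; share ≤4 is 2/2 = 100%.

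**Reading 3: `EVA` as the number of assessable patients.** The line is then one patient's score divided by n.

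**All three on ten invented scores** (2.5, 3.2, 3.6, 4.0, 4.0, 3.9, 3.1, 4.4, 4.6, 4.9; all assessable):
- Reading 1 returns the ten scores unchanged.
- Reading 2 gives 38.2/10 = 3.82.
- Reading 3 gives 0.25 to 0.49 per patient.
- Section 8 gives 7/10 = 70%.

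**What correct code should return.** With the feasibility study's 72% applied to 300 assessable patients, 0.72 × 300 = 216. The defined result is 216/300 = 72.0%, with an exact binomial 95% CI of 66.6% to 77.0%. The 72% comes from people aged 65 and over, so it illustrates population A only.

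**The case against.** The strongest objection is that nothing would go wrong in practice. The calculation is set out in full in the protocol and in SAP section 8. SAP 9.1 itself states the ≤4 rule above the table and again in the row label. The cell may be shorthand for deriving the score and then a rate over assessable patients, and characters may have been lost when the table was read from PDF. A programmer would follow the words. Most of this stands, and it is why the point is minor. It does not rescue the line, however: no reading gives the percentage until a ≤4 step is added, and nothing shows that such a step was lost.

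A reader might infer more than the documents support, in three ways.
- **That the primary percentage would be biased by some number of points.** One can construct such a figure by supposing that someone later adds the cut-off but drops the restriction to `EVA`=1, so that non-assessable patients count as low. No document proposes this. The present cell contains `EVA`, and section 8 limits the analysis to assessable patients. Any such figure would depend on the assumed percentage and on how many patients are non-assessable. It would be zero when `EVA`=1 is kept, so it does not measure this error.
- **That the endpoint is ambiguous.** It is not, because the written definitions agree throughout.
- **That the missing A/B split in the cell is a further error.** Section 8 already requires separate analyses, and a derivation cell need not repeat that.

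**Conclusion.** The code cell in SAP 9.1 is wrong as written, and the point is minor. For assessable patients it returns a score between 1 and 5; aggregated, it returns the mean score. Neither carries the information in the defined endpoint. There is no bias in percentage points to report, because the output is not a percentage and would probably be recognised as wrong when first seen. The conclusion rests on `EVA` being the patient-level flag of Appendice 2, but reading it as a count does not change the result.

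**What to change.** Replace the `TAUX` line in SAP 9.1 with two steps that follow section 8:
1. For each patient: if `EVA`=1 then `LOW`=(`SCORE_GLO`<=4); otherwise `LOW` is missing.
2. In populations A and B separately: number with `LOW`=1 divided by number with `EVA`=1, expressed as a percentage, with the binomial 95% CI of section 6.2.

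Keep the `EVA`=1 condition explicit, because in SAS a missing score satisfies <=4. Use the same `LOW` variable for the tests in 6.3.2 and, with its cut-off varied, for the optional analysis in 6.3.1.

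The cost is the correction of one code cell. The endpoint definition, the conduct of the study and the sample size are unaffected.

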9.2. Secondary endpoints

The secondary endpoints include:

- The questionnaire on the use of digital tools will be described per item:
 - This questionnaire includes 10 items.
 - A Likert-type scale with five modalities of response is proposed (never, rarely, sometimes, often, always).
 - No overall score will be calculated
- The responses to the FCCHL scales and to the questionnaire on the use of the digital will also be described by sub-groups defined according to the patient's characteristics at baseline (age, sex, lifestyle, etc.).

9.3. Statistical software

The main statistical analyses will be performed using SAS v9.4. Other statistical software to produce graphics, for example, could be used.

Appendice 1

CREATION OF A NEW INDICATOR VARIABLE

Patients fulfilling inclusions and non-inclusion criteria will be considered as ELIGIBLE (ELI = 1).

New binary variable ELI

Label: "Eligible population"

ELI = 1 if the patient is eligible

ELI = 0 if the patient is not eligible

Criteria	eFORM variable	Control
Eligible population	C1I C2I C3I C4I C5I C6I C1NI C2NI	C1I NE 0 and C2I NE 0 and C3I NE 0 and C4I NE 0 and C5I NE 0 and C6I NE 0 AND C1NI NE 1 and C2NI NE 1

Appendice 2

CREATION OF A NEW INDICATOR VARIABLE

Patients fulfilling all 14 items of FCCHL scale will be considered as ASSESSABLE (EVA=1).

Variable binaire EVA

Label: "Assessable Population "

EVA= 1 if the patient is included in assessable population

EVA= 0 if the patient is not included in assessable population

Criteria	eFORM variable	Control
Eligible population	ELI	ELI = 1 AND
Assessable population	EVA NOT_MOT NOT_ECR NOT_CONT NOT_TPS NOT_LIRE INF_SOU INF_DIS INF_OBT INF_MED INF_QUO TRT_INF TRT_CRE TRT_COR TRT_DEC	NOT_MOT ne . and NOT_ECR ne . and NOT_CONT ne . and NOT_TPS ne . and NOT_LIRE ne . and INF_SOU ne . and INF_DIS ne . and INF_OBT ne . and INF_MED ne . and INF_QUO ne . and TRT_INF ne . and TRT_CRE ne . and TRT_COR ne . and TRT_DEC ne . Then EVA=1 Else EVA=0
